### Clinical treatment

19. **At each weekly visit, subjects will meet with a psychiatrist of study physician.** At Week 0, subjects will be randomized to L-DOPA vs. placebo according to a blocked randomization schedule developed by the study statisticians and supplied to the NYSPI pharmacy. Raters, clinicians, and participants will be blinded to treatment assignment, though clinicians will be able to break the blind in case of clinical emergency. Treatment allocation will be concealed by over-encapsulation of 25/100 sinemet tablets or placebo tablets, such that all study pills will appear identical. All subjects will take 1 pill three times daily regardless of their treatment assignment. Those assigned to L-DOPA will begin taking 37.5mg carbidopa/150 mg levodopa once daily (with placebo twice daily) for one week, then increase to 75mg carbidopa/300mg levodopa (37.5 mg carbidopa/150mg levodopa twice daily and placebo once daily) for one week, and finally increase to 112.5mg carbidopa/450mg levodopa (37.5 mg carbidopa/150mg levodopa three times daily and no placebo) for the final six weeks. Subjects assigned to placebo will take placebo three times daily throughout the study. The 1.5 25/100 sinemet pills that are needed to make up a dose of 150mg levodopa will be installed a single, overencapsulated pill by the pharmacy.

20. Each subject assigned to the L-DOPA arm will be titrated to 450mg L-DOPA unless they cannot tolerate higher doses, in which case subjects will have their dosage reduced to the maximum tolerable dose. We chose 450mg as the target dose based on its being the dose that met the target progression criteria in the R61

Phase of this project (increased dopamine release in the striatum and increased processing/gait speed) and was highly tolerable to subjects. Both in our Pilot study and the literature overall, L-DOPA is an extremely well tolerated medication at doses < 600mg, which is substantially less than the doses often reached in the treatment of Parkinson's disease (900-1200mg). L-DOPA has been administered to healthy subjects in single dose studies and found to be well-tolerated. In Parkinson's disease, a recent clinical trial published in the New England Journal of Medicine randomized patients to receive 150mg, 300mg, or 600mg L-DOPA for 40 weeks. No dyskinesias or other neuropsychiatric effects were observed that were greater than the placebo group.

### Assessments

21. Subjects are expected to have a screening/evaluation visit, pre-treatment PET/MRI scanning day(s) (for those receiving imaging), and weekly visits from Week 0-8.

22. The following measures will be collected weekly throughout the study: 24-item HRSD, CGI Severity and Improvement, Structured Pill Count Interview, Unified Parkinson's Disease Rating Scale (UPDRS) (questions 32 and 33 will be used in this study to assess the duration and disability of dyskinesias caused by L-DOPA), Treatment Emergent Side Effect Scale, and Inventory of Depressive Symptoms—Self Report (IDS-SR).

23. In addition, baseline processing and gait speed assessments will be repeated after **Weeks 1, 2, 5, and 8** at 1pm to control for time of day effects and the duration since the last morning L-DOPA dose (anticipated to be 4 hours). Processing speed will be assessed using the Digit Symbol test from the Wechsler Adult Intelligence Scale-III (WAISIII) (119) and the Pattern and Letter Comparison tests (120). These tests are all reliable and valid, with moderate to high loadings on the latent speed factor. A latent factor (and subsequent factor score) will be extracted from the 3-test battery pre- and post-treatment and used as the main outcome in the R61. By extracting a latent factor and factor loadings we will utilize a more pure measure of processing speed than if we used the raw scores from an individual test or a sum total score from the three raw scores combined (121-124).

24. Gait will be assessed as both a single and dual task (ST, DT) on a Gaitrite walkway system in the LLDC. For the ST, patients are instructed to walk at their usual or normal speed over the walking course. For the DT, patients are instructed to walk at their usual pace while simultaneously verbally listing as many animals as possible (fluency DT). In addition, a counting DT will be used in which patients are instructed to walk at their usual pace while simultaneously performing serial subtractions by threes starting at 100 (125). Patients will start and end at a point 2 meters from beginning of the course to eliminate acceleration and deceleration effects. Each ST and DT will be assessed two times with the average used in the analyses.

25. Activity levels will be monitored in real time throughout the 8 week duration study using the GT3X+ Activity Monitors from Actigraph and the ActiLife Enterprise Software. We will analyze the average energy expenditure level (total counts in kcal per day assessed over 8 days with partial first day and last day assessments discarded) recorded in the week prior to baseline and the week prior to the Week 8 visit. A 60-second epoch will be used, and the percentage of time spent as sedentary vs. moderately active will also be explored. The combination of the Work-Energy Theorem and the Freedson Equation to adjust for lower

caloric expenditures if necessary. We will purchase 10 GT3X+ Activity Monitors for repeated use by all of the R33 Phase subjects.

### End of study procedures

26. Following the 8 week duration treatment study, endpoint assessments of depressive symptoms, processing speed, and gait speed will be made. Subjects will undergo endpoint neuropsychological testing and post-L-DOPA MRI and PET scanning.

27. Once post-treatment research procedures are completed, patients will enter 3 month open treatment period provided free of charge as described below.

You can upload charts or diagrams if any

## **Criteria for Early Discontinuation**

### Criteria for Early Discontinuation

The risk of non-response or adverse events to L-DOPA during the study period is addressed by having close clinical follow up of study subjects and stringent withdrawal criteria. These criteria are (1) participant withdraws his or her consent; (2) significant clinical worsening as defined by a slowing assessment rating using the CGI-Improvement scale of 6 (worse) or 7 (much worse) for 2 consecutive visits; or (3) development of significant side effects or an adverse event. Any subjects meeting any of these criteria will be withdrawn from the study and treated clinically. Furthermore, subjects may be withdrawn if they repeatedly miss scheduled appointments or clinical worsening necessitates more intensive treatment. No treatment is currently available for slowing, so there is not a standard of care treatment to offer patients withdrawn from the study. Thus, withdrawn patients will be followed in the open treatment period, offered appropriate psychiatric treatments if they have any conditions requiring treatment (e.g., depression), and be referred to their internist for close medical follow up.

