## Specific Aims and Hypotheses

### Specific Aims and Hypotheses

We hypothesize that treatment with levodopa (L-DOPA) will improve depressive symptoms in LLD by enhancing striatal dopamine release and improving cognitive/motor slowing. In the R33 Phase, 90 adults aged > 60 years with (1) a DSM 5 depressive disorder, (2) significant depressive symptoms (CES-D > 10), and (3) decreased processing speed (0.5 SD below age-adjusted norms on the Digit Symbol Test or Trails A) or decreased gait speed (average walking speed over 15' course < 1m/s) will be receive 8 weeks of treatment with LDOPA 450mg. Subjects will be tested for engagement of molecular target by determining whether subacute (8 week) treatment with L-DOPA displaces [C]-raclopride on positron emission tomography (PET).

R33 Phase.

Aim 1: To determine whether L-DOPA improves depressive symptoms in older adults.

Hypothesis 1: Compared to placebo, L-DOPA administration will result in greater improvements in depressive symptoms (as measured by HRSD scores).

Hypothesis 2: Greater post-L-DOPA decreases in [C]-raclopride BP and increases in processing/gait speed will be associated with greater depressive symptom improvement.

Exploratory aims: To explore the role of inflammatory markers and Catechol-O-methyl-transferase (COMT) genotype in moderating L-DOPA induced changes in slowing and depressive symptoms.

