## **Assessment Instruments**

Create a table or give a brief description of the instruments that will be used for assessment

---

Structured Clinical Interview Diagnostic for DSM 5 (SCID) (114): this semi-structured diagnostic interview will allow determination of whether subjects meet selection criteria.

Cumulative Illness Rating Scale-Geriatric (CIRS-G) (112) will be filled out at baseline to measure chronic medical illness burden.

Subjects' current physical pain will be assessed weekly using a 100mm Pain Visual Analog Scale (VAS) and used as a covariate in analyses of gait speed (113).

Center for Epidemiologic Studies—Depression Scale (CES-D): depression screening measure chosen given its ease of administration and wide use in epidemiological studies.

MMSE: standard means of assessing global cognition. The SCID, CES-D, and MMSE will be measured at baseline for the purpose of subject selection, while the following measures will be collected weekly throughout the study.

24-item HRSD (115): standard measure of depression severity that measures changes in depressive symptoms, though L-DOPA effects on depression are not the focus of the R61 Phase.

CGI Severity and Improvement: scales measuring the clinician's view of subjects' global functioning that will provide a clinical assessment of subjects at each visit and help maintain safety by identifying clinical worsening.

Structured Pill Count Interview: assessment of study medication compliance accounting for each dose of prescribed study medication during the study period.

Blind Assessments rate clinician's and patient's guesses as to study drug assignment.

Unified Parkinson's Disease Rating Scale (UPDRS) (116): standardized, reliable, and valid instrument for assessing the severity of the clinical features of PD; questions 32 and 33 will be used in this study to assess the duration and disability of dyskinesias caused by L-DOPA. While we include this measure, we are not expecting to observe dyskinesias in healthy subjects or at the L-DOPA doses being used in this study. Typically, such L-DOPA side effects emerge only in patients who have had Parkinson's disease for a number of years and then only if the LDOPA dose is raised to 600 mg or more.

Treatment Emergent Side Effect Scale: standardized general checklist used in our clinic for monitoring side effects associated with medication treatment.

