## Research Related Delay to Treatment

Will research procedures result in a delay to treatment?

Yes

Maximum duration of delay to any treatment

None.

Maximum duration of delay to standard care or treatment of known efficacy

Since patients may be assigned to placebo and the effects of L-DOPA on depression in this population are currently unknown, there will be an 8-week duration delay to receiving an agent of known efficacy to treat depression posed by subjects' participation in this study.

Treatment to be provided at the end of the study

We will provide 3 months of additional free clinic visits following the end of this project. At the conclusion of the 3 week study, a non-study clinician in our research clinic will be given the data on the subject's response to L-DOPA. This clinician will discuss with each subject on a case-by-case basis the risks and benefits of continuing L-DOPA treatment as well as other treatment options if warranted. Those who have benefited from the treatment and have not had significant side effects may elect to continue receiving LDOPA after receiving an explanation of the potential risks of chronic administration. If they do not want to continue L-DOPA, it will be discontinued after a 3 day step-down withdrawal of the drug. Transferring after-study care to a non-study clinician protects against the development of bias in the study clinicians and offers optimal clinical care to the subjects at the study conclusion.

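### Mandatory withdrawal for clinical worsening is defined only by a slowing rating, although the trial tests depression against placebo; depressive worsening and suicide risk are covered only indirectly

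*Protocol*

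**What the plan says.** *Criteria for Early Discontinuation* (protocol) lists three grounds: withdrawn consent; "significant clinical worsening as defined by a slowing assessment rating using the CGI-Improvement scale", with a score of 6 or 7 at two visits in a row; and significant side effects or an adverse event. These are binding: "Any subjects meeting any of these criteria will be withdrawn from the study and treated clinically". A looser clause follows, under which "subjects may be withdrawn if they repeatedly miss scheduled appointments or clinical worsening necessitates more intensive treatment". The section then explains that "No treatment is currently available for slowing, so there is not a standard of care treatment to offer patients withdrawn from the study", and adds that withdrawn subjects move to the open treatment period and are offered psychiatric care for any condition that needs it, with depression as the example.

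The trial itself is about depression. Hypothesis 1 in *Specific Aims and Hypotheses* is that, compared with placebo, "L-DOPA administration will result in greater improvements in depressive symptoms (as measured by HRSD scores"). Under *Research Related Delay to Treatment* the protocol accepts that "there will be an 8-week duration delay to receiving an agent of known efficacy to treat depression". *Assessment Instruments* describes the CGI as a view of global functioning that "will provide a clinical assessment of subjects at each visit and help maintain safety by identifying clinical worsening".

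**The concern.** The rule that takes a worsening subject off treatment should rate the condition under treatment. Here it rates slowing, which the trial treats as a mechanism and a selection feature. The section's reasoning, that no standard treatment exists for slowing, does not carry over to depression, for which the protocol acknowledges agents of known efficacy and a delay in reaching them.

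At stake is the safety of subjects who enter free of recent antidepressant treatment, half of whom (45 of 90, SAP *Overview*) are planned to take placebo for 8 weeks. In *Risks/Discomforts/Inconveniences*, item 10, the protocol relies on dropping deteriorating subjects as one way of limiting the risk of placebo. For depression, no defined rule stands behind that assurance.

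**Working it through.** No figure in the plan bears on this, so the check sets the routes out of treatment side by side.

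| Route | Where | Binding? | Names depression or suicide risk as the trigger? | Threshold |
|---|---|---|---|---|
| Consent withdrawn | *Early Discontinuation*, criterion 1 | Yes | No | Not applicable |
| Clinical worsening | Criterion 2 | Yes | No, it rates slowing | CGI-Improvement 6 or 7, two consecutive visits |
| Side effects or adverse event | Criterion 3 | Yes | No | None |
| Worsening that needs more intensive treatment | Same section, later sentence | No | No | None |
| Lowest dose not tolerated | *Risks*, item 2 and procedures for minimizing risks | Yes | No | Daily 37.5 mg/150 mg |
| Deterioration on study | *Risks*, item 10 | Stated intent | Not as a trigger, though the sentence concerns depressed, non-suicidal subjects | None |
| Expressed suicidal ideation | *Risks*, item 1 and procedures for minimizing risks | Assessment is mandatory | Yes, but stopping study drug is not mentioned | Any expressed ideation |

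**Where depression limits do appear.** Total HRSD of 25 or more, HRSD suicide item > 2 and clinician-judged significant suicide risk are entry exclusions (*Inclusion/Exclusion Criteria*, exclusion 5; *Study Procedures*, Evaluation item 1). None is repeated as an on-study limit.

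**Tracing a case.** Take a subject who enters below those limits. At Week 4 the HRSD suicide item is above 2 and slowing is unchanged.

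1. Criterion 2 is not met, because it rates slowing.
2. Criterion 3 is met only if the site records the change as an adverse event. The protocol does not say whether it should.
3. The later sentence allows withdrawal but does not require it.
4. If ideation is expressed, the pathway brings immediate clinician assessment, with caregiver contact, same-day evaluation and treatment, or emergency evaluation and hospitalization as options. The status of study drug is left open.

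**Timing of criterion 2.** Visits are weekly. Taking Week 1 as the first rating of change from baseline (an assumption), two consecutive ratings are complete no earlier than Week 1 + 1 = Week 2. In general, a first bad rating at Week w triggers withdrawal at Week w + 1 at the earliest. Re-targeting criterion 2 would therefore cover sustained depressive worsening but would be too slow as the only rule for suicide risk.

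**Data needed for a better rule.** *Assessments*, item 22, states: "The following measures will be collected weekly throughout the study: 24-item HRSD, CGI Severity and Improvement". A depression or suicide-item trigger can be read from ratings already planned.

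**The case against.** The strongest reply is that criterion 3 already supplies a mandatory route. It carries no causality test, scale or waiting period, and the protocol lists suicidal ideation and worsening on placebo among the study's own risks. Recording significant emergent suicide risk as an adverse event would be ordinary practice. This stands as far as it goes: such an event, once recorded, requires withdrawal. But the protocol does not define the term or say that worsening of the condition under study counts. Read literally, the criterion would also withdraw a subject for mild nausea, which 44% reported in the single-dose study described under *Risks*, item 2. It will have to be applied with judgement, and so does not work as a depression rule.

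Several other points also stand. Weekly physician visits and emergency unblinding are in place (*Clinical treatment*, item 19). Entry requires HRSD below 25 and no suicidal ideation, and subjects must have discussed standard treatments and prefer not to start one. These lower the risk and support clinical response. They do not define what ends treatment.

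A reader might infer from the three listed criteria that suicidality is unmanaged, or that a subject with worsening depression cannot be withdrawn. The documents contradict both: the ideation pathway, the discretionary clause and the offer of depression treatment after withdrawal are all written down.

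**Conclusion.** The point holds as a mismatch of construct. The only mandatory rule that defines clinical worsening uses slowing, in a placebo-controlled trial of depression, and it narrows an instrument that the protocol elsewhere gives a global safety role. Depressive worsening and emergent suicide risk are reached only through routes that are discretionary, unquantified, dependent on how an event is recorded, or silent on study drug.

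The size cannot be given as a number. The documents state no rate of emergent suicide risk. Even an assumed rate would count cases arising, not cases kept on study drug because of this wording; that second number is unknown and could be small. A reader might also infer bias in the treatment comparison. Nothing in the documents establishes that, and none is claimed. The conclusion rests on the text and on one reading: that an adverse event is not automatically understood to include worsening of the depression under study. The change is worth making because it is a patient-safety gain at low cost.

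**What to change.** In *Criteria for Early Discontinuation*:

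- Define criterion 2 as CGI-Improvement 6 or 7 on global or depressive state at two consecutive visits. Keep slowing as a separate limb if wanted.
- Add a mandatory stop of study drug, with clinical treatment, at any single visit with HRSD suicide item > 2 or clinician-judged significant suicide risk. The wording can be taken from exclusion 5.

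Optionally, state that stopping study drug does not end assessment, so that weekly HRSD continues to Week 8 where the subject agrees and any new treatment is recorded. This needs one added SAP sentence on how scores after rescue treatment enter the mixed model.

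The two core changes affect one protocol section and need no new instrument or visit. The downside is possibly a few more discontinuations. A fixed cutoff on the suicide item also takes some discretion from the clinician, which is reasonable here because the protocol already uses the same cutoff to refuse entry.

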## **Blood and other Biological Samples**

Please create or insert a table describing the proposed collection of blood or other biological specimens. A 20cc blood sample will be drawn at baseline. General medical tests will be performed, such as CBC, Chem 7, LFTs, TSH, cholesterol, B12, and folate. Also, tubes of whole blood will be aliquoted and frozen for subsequent measurement of (1) serum inflammatory markers and (2) IL-6 and COMT genotypes.

## **Assessment Instruments**

Create a table or give a brief description of the instruments that will be used for assessment

---

Structured Clinical Interview Diagnostic for DSM 5 (SCID) (114): this semi-structured diagnostic interview will allow determination of whether subjects meet selection criteria.

Cumulative Illness Rating Scale-Geriatric (CIRS-G) (112) will be filled out at baseline to measure chronic medical illness burden.

Subjects' current physical pain will be assessed weekly using a 100mm Pain Visual Analog Scale (VAS) and used as a covariate in analyses of gait speed (113).

Center for Epidemiologic Studies—Depression Scale (CES-D): depression screening measure chosen given its ease of administration and wide use in epidemiological studies.

MMSE: standard means of assessing global cognition. The SCID, CES-D, and MMSE will be measured at baseline for the purpose of subject selection, while the following measures will be collected weekly throughout the study.

24-item HRSD (115): standard measure of depression severity that measures changes in depressive symptoms, though L-DOPA effects on depression are not the focus of the R61 Phase.

CGI Severity and Improvement: scales measuring the clinician's view of subjects' global functioning that will provide a clinical assessment of subjects at each visit and help maintain safety by identifying clinical worsening.

Structured Pill Count Interview: assessment of study medication compliance accounting for each dose of prescribed study medication during the study period.

Blind Assessments rate clinician's and patient's guesses as to study drug assignment.

Unified Parkinson's Disease Rating Scale (UPDRS) (116): standardized, reliable, and valid instrument for assessing the severity of the clinical features of PD; questions 32 and 33 will be used in this study to assess the duration and disability of dyskinesias caused by L-DOPA. While we include this measure, we are not expecting to observe dyskinesias in healthy subjects or at the L-DOPA doses being used in this study. Typically, such L-DOPA side effects emerge only in patients who have had Parkinson's disease for a number of years and then only if the LDOPA dose is raised to 600 mg or more.

Treatment Emergent Side Effect Scale: standardized general checklist used in our clinic for monitoring side effects associated with medication treatment.

Inventory of Depressive Symptoms—Self Report (IDS-SR) (117): rating scale for depressive symptoms based on DSM criteria that has been increasingly used in antidepressant studies due to its equivalent weightings for each item, understandable anchor points, and inclusion of all DSM criteria (118).

Processing speed will be assessed using the Digit Symbol test from the Wechsler Adult Intelligence Scale-III (WAIS-III) (119) and the Pattern and Letter Comparison tests (120). These tests are all reliable and valid, with moderate to high loadings on the latent speed factor.

Episodic memory functioning will be assessed using the Wechsler Memory Scale Logical Memory Test I & II (153). Inclusion of this test will allow us to identify deficits in episodic memory functioning consistent with a classification of amnesic mild cognitive impairment (aMCI) (7).

Executive function will be assessed via the NIH-EXAMINER battery designed to assess executive functions reliably, comprehensively, and efficiently (154-155). This battery examines working memory, inhibition, set shifting, fluency, insight, planning, social cognition and behavior.

The Short Physical Performance Battery (SPPB) (156), a performance measure of gait, balance, and lower extremity strength sensitive to meaningful change.

The 36-item self-report World Health Organization Disability Assessment Schedule 2.0 (WHODAS2) provides a global measure of disability and 7 domain-specific scores based on the conceptual framework of the International Classification of Functioning, Disability, and Health (ICF) (157).

The self-report 38-item Measure of Everyday Cognition (ECog) is adapted from an informant-report version and measures impairment and change in domains of everyday/real-world functioning relevant to 7 specific neuropsychological domains (158).

The Falls Efficacy Scale-International will assess subjects' fear of falling weekly using a 16-item scale rating respondents' confidence (1 not at all concerned—4 very concerned) in doing daily tasks without falling (159-160).

Please attach copies, unless standard instruments are used

